12.3 Publication of study protocol and results

The key design elements of this protocol will be posted in a publicly accessible database such as clinicaltrials.gov. In addition, upon study completion and finalization of the study report the results of this trial will be either submitted for publication and/or posted in a publicly accessible database of clinical trial results.

12.4 Quality Control and Quality Assurance

Novartis maintains a robust Quality Management (QM) system that includes all activities involved in quality assurance and quality control, including the assignment of roles and responsibilities, the reporting of results, and the documentation of actions and escalation of issues identified during the review of quality metrics, incidents, audits and inspections.

Audits of investigator sites, vendors, and Novartis systems are performed or overseen by Novartis Pharma Auditing and Compliance Quality Assurance (or CRO working on behalf of Novartis), a group independent from those involved in conducting, monitoring or performing quality control of the clinical trial. The clinical audit process uses a knowledge/risk based approach.

Audits are conducted to assess GCP compliance with global and local regulatory requirements, protocols and internal SOPs, and are performed according to written Novartis processes.

13 Protocol adherence

This protocol defines the study objectives, the study procedures and the data to be collected on study participants. Additional assessments required to ensure safety of patients should be administered as deemed necessary on a case by case basis. Under no circumstances is an investigator allowed to collect additional data or conduct any additional procedures for any research related purpose involving any investigational drugs under the protocol.

Investigators ascertain they will apply due diligence to avoid protocol deviations. If an investigator feels a protocol deviation would improve the conduct of the study this must be considered a protocol amendment, and unless such an amendment is agreed upon by Novartis and approved by the IRB/IEC and health authorities, where required, it cannot be implemented.

Isolated ALT or AST elevation > 5 to ≤ 8 × ULN	
 If confirmed, consider interruption or discontinuation of study drug If elevation persists for more than 2 weeks, discontinue the study drug Establish causality Complete CRFs per liver event guidance*
Isolated ALT or AST elevation > 3 to ≤ 5 × ULN (patient is asymptomatic)	
 Monitor liver chemistry tests two or three times weekly
Isolated ALP elevation	
 Repeat liver chemistry tests within 48-72 hours If elevation is confirmed, measure fractionated ALP; if >50% is of liver origin, establish hepatic causality Complete CRFs per liver event guidance* Consider study treatment interruption or discontinuation
Any AE potentially indicative of liver toxicity	
 Hospitalize if clinically appropriate Complete CRFs per liver event guidance*

*Liver event guidance for CRF completion is available in the Site Operations Manual

Note: In exceptional cases when a hepatologist considers a liver biopsy, it is strongly recommended to make specimen slides available for evaluation by Novartis to potentially identify project-wide patterns of hepatotoxicity.

Table 15-3 Exclusion of underlying liver disease

Disease	Assessment
Hepatitis A, B, C, E	
 • IgM anti-HAV; HBSAg, IgM anti-HBc, HBV DNA; anti-HCV, HCV RNA, IgM & IgG anti-HEV, HEV RNA
CMV, HSV, EBV infection	
 • IgM & IgG anti-CMV, IgM & IgG anti-HSV; IgM & IgG anti-EBV
Autoimmune hepatitis	
 • ANA & ASMA titers, total IgM, IgG, IgE, IgA
Alcoholic hepatitis	
 • Ethanol history, GGT, MCV, CD-transferrin
Nonalcoholic steatohepatitis	
 • Ultrasound or MRI
Hypoxic/ischemic hepatopathy	
 • Medical history: acute or chronic CHF, hypotension, hypoxia, hepatic venous occlusion. Ultrasound or MRI.
Biliary tract disease	
 • Ultrasound or MRI, ERCP as appropriate.
Wilson disease	
 • Caeruloplasmin
Hemochromatosis	
 • Ferritin, transferrin
Alpha-1-antitrypsin deficiency	
 • Alpha-1-antitrypsin

16 Appendix 2: Specific Renal Alert Criteria and Actions

Criteria	Action required
Serum creatinine (sCr) increase 25 – 49% compared to baseline	
 Consider causes and possible interventions Follow up within 2-5 days
Serum creatinine increase \geq 50%	
 Consider causes and possible interventions Repeat assessment within 24-48h if possible Consider drug interruption or discontinuation unless other causes are diagnosed and corrected Consider hospitalization and specialized treatment
Protein-creatinine or albumin-creatinine ratio increase \geq 2-fold	
 Consider causes and possible interventions Assess serum albumin & serum protein Repeat assessment to confirm
or	
new onset dipstick proteinuria \geq 1+	
 Consider drug interruption or discontinuation unless other causes are diagnosed and corrected
or	
Albumin-creatinine ratio (ACR) \geq 30 mg/g or \geq 3 mg/mmol;	
or	
Protein-creatinine ratio (PCR) \geq 150 mg/g or $>$ 15 mg/mmol	
New onset glucosuria on urine dipstick (unless related to concomitant treatment, diabetes)	
Assess & document:
 
 Blood glucose (fasting) Serum creatinine Urine albumin-creatinine ratio
	
Assess & document:
 
 Urine sediment microscopy
New hematuria on dipstick	
 Assess sCr and urine albumin-creatinine ratio Exclude infection, trauma, bleeding from the distal urinary tract/bladder, menstruation Consider bleeding disorder

Specific Renal Alert Criteria and Actions

Additional specialized assessments are available to assess renal function or renal pathology. Note: In exceptional cases when a nephrologist considers a renal biopsy, it is strongly recommended to make specimen slides available for evaluation by Novartis to potentially identify project-wide patterns of nephrotoxicity.

Whenever a renal event is identified, a detailed patient history and examination are indicated to identify, document and potentially eliminate risk factors that may have initiated or contributed to the event:

- Blood pressure assessment (after 5 min rest, with an appropriate cuff size)
- Signs and symptoms such as fever, headache, shortness of breath, back or abdominal pain, dysuria, hematuria, dependent or periorbital edema
- Changes in blood pressure, body weight, fluid intake, voiding pattern, or urine output
- Concomitant events or procedures such as trauma, surgical procedures, cardiac or hepatic failure, contrast media or other known nephrotoxin administration, or other potential causes of renal dysfunction, e.g., dehydration, hemorrhage, tumor lysis

Table 16-1 Follow-up of renal events

Action	Follow up
Assess*, document and record in the Case Report Form (CRF) or via electronic data load. Review and record possible contributing factors to the renal event (co-medications, other co-morbid conditions) and additional diagnostic procedures (MRI etc) in the CRF.	
 • Urine dipstick and sediment microscopy • Blood pressure and body weight • Serum creatinine, electrolytes (sodium, potassium, phosphate, calcium), bicarbonate and uric acid • Urine output • Event resolution: (sCr within 10% of baseline or protein-creatinine ratio within 50% of baseline)
Monitor patient regularly (frequency at investigator's discretion) until:	
or
 
 • Event stabilization: sCr level with $\pm 10\%$ variability over last 6 months or protein-creatinine ratio stabilization at a new level with $\pm 50\%$ variability over last 6 months.

* Urine osmolality: in the absence of diuretics or chronic kidney disease this can be a very sensitive metric for integrated kidney function that requires excellent tubular function. A high urinary osmolality in the setting of an increase in sCr will point toward a "pre-renal" cause rather than tubular toxicity.

1.1 Scope of document

The RAP documents contain detailed information to aid the production of Statistics & Programming input into the Clinical Study Report (CSR) for trial “**CLLG783X2201**”.

The Statistical analysis plan (SAP) describes the implementation of the statistical analysis planned in the protocol.

Tables, Figures, Listings (TFL) details the presentation of the data, including shells of summary tables, figures and listings, and Programming Datasets Specification (PDS) contains programming specifications e.g. for derived variables and derived datasets, to support the creation of CSR and IA outputs.

1.2 Study reference documentation

Final study protocol (version v00) is available at the time of finalization of Statistical Analysis Plan.

1.3 Study objectives

1.3.1 Primary objective(s)

Primary objective(s)	Endpoints related to primary objectives

 To evaluate the safety and tolerability of LLG783 in subjects with PAD and intermittent claudication after 16 weeks of exposure to LLG783. 	
 AEs (including observations made during physical examinations as appropriate) 
 Incidence Severity Vital signs including: 
 Pulse rate Blood pressure (BP) Respiratory rate Body temperature Laboratory evaluations 
 Hematology Clinical chemistry Urinalysis Electrocardiogram (ECG) intervals

 To evaluate the effect of LLG783 on functional capacity after 3 months of treatment in subjects with PAD and intermittent claudication. 	
 Maximum walking distance assessed by 6-minute walk test (6MWT)

1.3.2 Secondary objective(s)

Secondary objective(s)	Endpoints related to secondary objectives
------------------------	---

• To investigate the PK of LLG783 in subjects with PAD and intermittent claudication.	
• PK parameters will be determined, including: AUCinf, AUClast, AUC0-t, AUC0tau, Cmax and Tmax

• To evaluate the effect of LLG783 on symptomatic functional capacity after 3 months of treatment in subjects with PAD and intermittent claudication.	
• Pain-free walking distance assessed by 6MWT

Corporate Confidential Information

Corporate Confidential Information

1.4 Study design and treatment

[figure not shown]
This is a non-confirmatory, randomized, subject and investigator-blinded, placebo-controlled, parallel-group study in subjects with PAD and intermittent claudication.

Approximately 40 randomized subjects will be treated in a 1:1 ratio to receive LLG783 or placebo as an i.v. infusion of CCI i.v. dosing once every 4 weeks for a total of 4 doses over a period of 12 weeks/3 months.

The dose may be altered based on review of data from the 1st interim analysis (IA).

Corporate Confidential Information

Figure 1-1 Study design

It is intended that the s.c. study participants would maintain the same assessment visit schedule as the i.v. dosed study participants.

Subjects who discontinue the study for reasons other than safety prior to the week 16 visit may be replaced to ensure ability to assess 40 subjects with a functional assessment after 16 weeks of exposure.

2 First interpretable results (FIR)

Corporate Confidential Information

FIR **Corporate Confidential Information** will focus on the following analyses:

1. Subject disposition **Corporate Confidential Information**
2. Demographics and baseline characteristics **Corporate Confidential Information**
3. Safety results **Corporate Confidential Information**
 - Number and percentage of subjects with adverse events by preferred term.
 - Overall incidence of AEs.
4. Efficacy results **Corporate Confidential Information**
 - Arithmetic mean (80% CI) of 6MWT parameters vs time profile by treatment.
 - MMRM model analysis of 6MWT parameters.
 - Model estimated means of 6MWT parameters over time.
5. Pharmacokinetic results for Plasma **Corporate Confidential Information**
 - Arithmetic mean (SD) concentration-time plot.
 - Summary statistics for PK parameters.
6. Immunogenicity Data **Corporate Confidential Information**

3 Interim analyses

There are 2 planned IAs in this study. It is planned to conduct the first IA (IA1) once approximately 12 subjects reach 8 weeks following the first dose. The purpose of IA1 will be to assess the PK of LLG783 to make a dose adjustment should the exposure be significantly lower or higher than expected.

Corporate Confidential Information

Corporate Confidential Information

Unblinded IA results will be reviewed by the clinical team. The clinical team may communicate interim results (e.g. evaluation of efficacy criteria or information needed for planning/modifying another study) to relevant Novartis teams for information, consulting and/or decision purposes.

Corporate Confidential Information

Additional interim analyses may be conducted to support decision making concerning the current clinical study, the sponsor's clinical development projects in general or in case of any safety concerns. In this case, the analyses as described in the sections below are conducted for the relevant endpoints.

Corporate Confidential Information

4 Statistical methods: Analysis sets

For subjects whose actual treatment received does not match the randomized treatment, the treatment actually received will be used for the analysis.

The safety analysis set will include all subjects that received any study drug.

The PK analysis set will include all subjects with at least one available valid (i.e. not flagged for exclusion) PK concentration measurement, who received any study drug and experienced no protocol deviations with relevant impact on PK data.

The PD analysis set will include all subjects with any available PD data, who received any study drug and experienced no protocol deviations with relevant impact on PD data.

The analysis sets and protocol deviation codes are related as follows:

Table 4-1 Protocol deviation codes and analysis sets

Category Deviation code	Text description of deviation	Data exclusion
	Subjects are excluded from PD analysis in case of these PDs:	Exclude subject from PD analysis set
COMD03	Change in type or dosage of narcotic pain relievers; OR Change in type or dosage of PAD specific symptom-relief drugs prior to week 16 of study.	
Inc05	Deviation from inclusion criterion 5 – Moderately impaired ambulatory function due primarily to PAD and maximum walk distance between 50 and 400 meters.	
Exc02	Deviation from exclusion criterion 2 – Pregnant or nursing (lactating) women.	
Exc05b	Deviation from exclusion criterion 05b – Chronic heart failure New York Heart Association Class III or IV.	
Exc14	Deviation from exclusion criterion 14 – Patients unable to hold all narcotic pain relievers for 24 hours prior to performance of the 6MWT.	
Inc03	Deviation from inclusion criterion 3 - On stable medical therapy for at least 4 weeks prior to the screening visit.	
Exc03	Deviation from exclusion criterion 3 – Patients who meet the specific PAD related exclusion criteria.	

If updates to this table are needed, an amendment to the SAP needs to be implemented prior to DBL.

Dose adjustment might occur as part of the IA1 safety and tolerability conclusions. In case of dose adjustment occurring during the study, subjects will be analyzed under first dose received, censoring any observations post dose adjustment (if any) in statistical models and descriptive summaries. Further updates on the SAP analysis strategy described below may be needed, depending on the findings of the IA1 and the proposed changes to the dosing strategy.

5 Statistical methods for Pharmacokinetic (PK) parameters

All subjects within the PK analysis set will be included in the PK data analysis.

In case of dose adjustment occurring during the study, subjects will be analyzed under first doses received, censoring any observations post dose adjustment (if any) in descriptive summaries.

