3.1 Study design

Figure 3-1 Study Design

This is a non-confirmatory, randomized, patient and investigator-blinded, placebo-controlled, parallel-group study in patients with PAD and intermittent claudication. Approximately 40 randomized patients will be treated in a 1:1 ratio to receive LLG783 or placebo as an i.v. infusion of CCI i.v. dosing once every 4 weeks for a total of 4 doses over a period of 12 weeks/3 months. Key study assessments are conducted at week 16 (month 4) of the study (i.e. after 16 weeks of exposure), which is one month after the final dose of study medication.

The dose may be altered based on review of data from the 1st interim analysis (IA).

Corporate Confidential Information

Potential study participants will undergo screening assessments, including 6MWT and ABI, to determine eligibility. Patients who pass the screening evaluations will come to the investigational site on Day 1, at which time inclusion and exclusion criteria will be re-reviewed, and eligible patients will be randomized and dosing will commence.

Assessments of functional capacity (6MWT) will be made at weeks 8 and 16 (days 57 and 113) following the first dose of study medication, with follow-up functional assessments at weeks 24 and 32 (days 169 and 225) following the first dose of study medication (i.e. 2 and 4 months following the last dose of medication, see [Figure 3-1](#)). These follow-up assessments will be performed to help define durability of clinical response as LLG783 exposure declines. The primary endpoint of improved walk distance will be adjudicated based on the 8 and 16 week data points, though the 24 and 32 week data may be used in final statistical modeling.

Safety assessments will include physical examinations, ECGs, vital signs, standard clinical laboratory evaluations (hematology, blood chemistry, and urinalysis), as well as AE and SAE monitoring.

Patients who discontinue the study for reasons other than safety prior to the week 16 visit may be replaced in order to ensure ability to assess 40 patients with a functional assessment after 16 weeks of exposure.

Corporate Confidential Information

Corporate Confidential Information

Corporate Confidential Information

Corporate Confidential Information

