11.1 Analysis sets

For all analysis sets, patients will be analyzed according to the study treatment(s) received.

The safety analysis set will include all patients that received any study drug.

The PK analysis set will include all patients with at least one available valid (i.e. not flagged for exclusion) PK concentration measurement, who received any study drug and with no protocol deviations that impact on PK data.

The PD analysis set will include all patients with available PD data and no protocol deviations with relevant impact on PD data.

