11.4.3 Handling of missing values/censoring/discontinuations

The primary analysis will be based on all patients with a baseline MWD and at least one post-baseline MWD. Patients who undergo any lower extremity vascular interventions (angioplasty, stenting, or bypass surgery) before the Week 16 efficacy assessment or patients who drop out for other reasons before this assessment may be replaced to ensure 40 patients complete this primary endpoint assessment. Data from such patients will be included in the model for the primary analysis until the time of dropout or intervention; no imputation of the missing data will be performed for the primary analysis.

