5.2 Descriptive analyses

LLG783 serum concentrations will be listed by treatment, subject, and visit/sampling time point. Descriptive summary statistics will be provided by treatment and visit/sampling time point, including the frequency (n, %) of concentrations below the LLOQ (and above the ULOQ) and reported as zero. Pharmacokinetic parameters will be listed by treatment and subject and summarized by treatment and visit. Summary statistics will include mean (arithmetic and geometric), SD, CV (arithmetic and geometric), median, minimum and maximum. An exception to this is T_{max} where median, minimum and maximum will be presented.

Concentrations below LLOQ will be treated as zero in summary statistics and for PK parameter calculations. A geometric mean will not be reported if the dataset includes zero values.

Arithmetic mean (SD) serum concentration by time will be plotted on linear-linear and log-linear scale (all treatment groups in the same graph).

Overlaying individual serum concentration by time profile, by treatment will be plotted (one graph per treatment group, all subjects in the same graph) on linear-linear and log-linear scale.

Individual serum concentration by time profile, by subject will be plotted on linear-linear and log-linear scale (one graph per treatment group and subject).

6 Statistical methods for Efficacy/Pharmacodynamic (PD) parameters

All subjects within the PD analysis set will be included in the PD data analysis.

In case of dose adjustment occurring during the study, subjects will be analyzed under first doses received, censoring any observations post dose adjustment (if any) in statistical models and descriptive summaries.

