6.1.1 Variables

The primary efficacy endpoint is the Maximum walking distance (MWD) defined as the total distance walked in 6 minutes as assessed by the 6MWT and will be used to evaluate functional capacity of PAD subjects participating in this study.

Change from baseline in MWD will also be derived. Baseline will be taken from the screening 6-minute walk test.

6MWT data will be excluded from primary and secondary analyses under below conditions:

- within 24 hours after narcotic pain medication
- the very first 6MWT after the adverse event of COPD exacerbation
- all tests after post baseline stent or angioplasty procedures
- Lap distance for the 6MWT significantly shorter than the recommended length of 50-70m

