6.1.3.1 Model checking procedures

Handling of missing values/censoring/discontinuations

The primary analysis will be based on all subjects with a baseline MWD and at least one post baseline MWD. Subjects who undergo any lower extremity vascular interventions (angioplasty, stenting, or bypass surgery) before the Week 16 efficacy assessment or subjects who drop out for other reasons before this assessment may be replaced to ensure 40 subjects complete this primary endpoint assessment. Data from such subjects will be included in the model for the primary analysis until the time of dropout or intervention; no imputation of the missing data will be performed for the primary analysis.

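### A narcotic or PAD symptom-drug change before Week 16 (COMD03) removes the whole patient from the walking-distance analyses, including a Week 8 test done before the change, and no visible sensitivity analysis restores the patient

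*SAP*

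**What the plan says.** SAP section 4, Table 4-1, gives the protocol deviations that lead to exclusion. Code COMD03 covers a change in narcotic pain relievers or a "Change in type or dosage of PAD specific symptom-relief drugs prior to week 16 of study". The action is "Exclude subject from PD analysis set", so the unit removed is the patient, not the visit. SAP section 6 then states: "All subjects within the PD analysis set will be included in the PD data analysis". SAP 6.2.3 analyses pain-free walking distance in the same way as maximum walking distance (MWD).

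The general principle comes from protocol 11.1: "The PD analysis set will include all patients with available PD data and no protocol deviations with relevant impact on PD data". Protocol Table 5-1 prohibits these drug changes through Week 16. It asks that the sponsor be told, so that stopping treatment and replacing the patient can be considered.

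SAP 6.1.3.1 describes the primary population without naming the PD set: "The primary analysis will be based on all subjects with a baseline MWD and at least one post baseline MWD". Protocol 11.4.3 has almost the same sentence.

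Other events are handled more narrowly. SAP 6.1.1 begins a list with "6MWT data will be excluded from primary and secondary analyses under below conditions". It drops a test done within 24 hours of a narcotic, and drops only the later tests after a stent or angioplasty. SAP 6.1.3.1 keeps data up to dropout or vascular intervention. SAP section 4 censors only observations after a dose adjustment.

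**The concern.** The 6-minute walk tests relevant to the primary endpoint fall on Days 57 and 113 (protocol 3.1). If a patient's cilostazol dose changes on Day 80, the Day 57 test is unaffected by the change, yet COMD03 removes it with the patient. A patient who has an angioplasty on Day 80 keeps that test.

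The other codes in Table 4-1 concern entry criteria. COMD03 also covers events after randomisation, and the drugs involved treat pain or walking symptoms in a trial whose endpoint is walking. If the decision to change drugs depends on how the patient is walking, the patients who remain are a selected group. When the drug works, the selection need not be the same in the two arms. The result is judged at Week 16 on whether the 80% confidence limit exceeds 0 and whether the estimate reaches 50 m. The second criterion is a threshold on the point estimate, so a shift of a few metres counts.

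The LOCF and WOCF runs in SAP 6.1.3.3 repeat the primary analysis with missing values filled in. They do not bring back patients outside the PD set.

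**Working it through.** The visible text gives no SD, correlation, rate of drug change or reason for change, so there is no figure in the plan to reproduce. The check shows how the rule acts and gives a range under stated assumptions.

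**Identity.** If a fraction q of an arm is removed, and those kept differ from those removed by D metres on average, the arm mean moves by q × D. The treatment difference therefore moves by q(LLG783) × D(LLG783) − q(placebo) × D(placebo). For scale, removing 2 of 20 patients with D = 50 m moves one arm by 0.10 × 50 = 5 m.

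**Inputs from the documents:** about 40 patients randomised 1:1 (20 per arm), and the 50 m threshold.

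**Assumptions:** true difference 50 m at Week 16 and 35 m at Week 8; SD of change 40, 60 or 80 m; visit correlation 0.7; normal changes; the same rule in both arms; no replacement. The target is the Week 16 difference had no drug change occurred. The baseline covariate and the Week 24 and 32 visits are left out.

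**Standard error with full data:** SD × √(2/20), which is 12.6, 19.0 and 25.3 m.

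**One case by hand.** Suppose 25% of patients whose Week 16 change is below 80 m change drugs, with SD 60 m. With z = (80 − mean)/60, q = 0.25 × Φ(z) and the arm mean rises by 60 × 0.25 × φ(z)/(1 − q).
- Placebo: z = 1.333, q = 0.25 × 0.909 = 0.227, rise = 15 × 0.164/0.773 = 3.2 m.
- LLG783: z = 0.5, q = 0.25 × 0.691 = 0.173, rise = 15 × 0.352/0.827 = 6.4 m.
- Shift in the difference: 6.4 − 3.2 = +3.2 m.

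Fewer LLG783 patients leave, but they differ more from those who stay, so the shift is upward. Under a logistic rule in which poor walkers change drugs, the larger placebo fraction dominates and the shift is downward.

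**Range over SD 40 to 80 m:**

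| Assumed driver of the drug change | Placebo changing | Shift from excluding the patient |
|---|---|---|
| Unrelated to walking | any | 0 |
| Poor Week 8 change, logistic | 10–20% | −1.3 to −5.2 m |
| Good Week 8 change, logistic | 10–20% | −1.9 to −3.2 m |
| Poor Week 16 change, logistic | 10–20% | −2.4 to −9.9 m |
| Step: 12 or 25% if Week 16 change is below 40–120 m | 8–25% | +0.3 to +3.4 m |
| Step: 12 or 25% if Week 8 change is below 40–100 m | 8–25% | +0.3 to +1.7 m |

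The logistic slopes are 1 or 2 log-odds per SD for poor walkers and 1 for good walkers. The largest shift is about 0.6 of the standard error. With no drug effect the shift is about 0, and criterion 1 is met in about 10% of simulated trials with or without the exclusion.

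**Criterion 2, SD 60 m.** With a true difference of 60 m, the chance of an estimate of at least 50 m is 0.70 with full data, 0.49 to 0.66 under the logistic rules and 0.71 to 0.73 under the step rules. With a true difference of 40 m the figures are 0.30, 0.17 to 0.28 and 0.34 to 0.37.

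**Precision.** If changes are unrelated to walking, the standard error grows by 1/√(1 − q): about 5% at q = 0.10 and 12% at q = 0.20.

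**Dropping only later tests.** If every change follows the Week 8 test, the bias is about 0 when Week 8 walking drives the change. It is roughly halved (−1.2 to −5.6 m) when the not yet observed Week 16 change does. If half of the changes come before the Week 8 test (SD 60 m, 20% changing, slope 2), about 2 of 5 m remains in the first case and about 7 of 9 m in the second. If all come before it, nothing is gained.

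**The case against.** The rule is deliberate and fixed in advance. Protocol 11.1 limits the PD set to patients without relevant deviations, and Table 5-1 prohibits these changes. The trial is non-confirmatory, and excluding protocol deviators is in part a choice of estimand. The contrasting events are also not identical in kind: vascular intervention is permitted when clinically indicated, and dose adjustment is a sponsor decision. All of this stands, and it is why the point is a request for improvement and not a charge of error. But pre-specification only prevents a choice made after seeing results; it does not undo selection on an event after randomisation.

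The change rates are also assumed and may be too high, since patients enter on stable therapy. That stands too.

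A reader might infer more than the documents support:
- *That SAP 6.1.3.1 and protocol 11.4.3 plainly contradict Table 4-1.* They can be read as applying within the PD set. A patient discontinued and replaced under Table 5-1 might also fall under the dropout sentence, which keeps earlier data. The wording is ambiguous and needs reconciling.
- *That the rule favours LLG783.* Most assumed cases shift the estimate towards no effect, and the sign depends on a relation that the documents do not describe.
- *That the bias reaches about 12 m either way.* This needs the rule to act in one arm only, which nothing supports in a trial where patients and investigators are blinded.
- *That no restoring sensitivity analysis exists.* Parts of the SAP are withheld, so only the visible text can be judged.
- *That replacing patients cures it.* Replacement restores precision (with 20% unrelated changes at SD 60 m, the standard error falls from 21.3 to 19.1 m) but does not remove the selection.

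**Conclusion.** The point holds as a should-fix. Read with SAP section 6, COMD03 takes the whole patient out of the primary and secondary walking analyses. For a change between Day 57 and Week 16 it discards a valid earlier test that the SAP would keep after a stent, an intervention, a dropout or a dose adjustment. No sensitivity analysis in the visible text shows whether the conclusion depends on this.

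Confidence is high on the text and low on the direction and size of any bias. The range of about -10 to +3.5 m rests wholly on the assumptions listed above. It stays below one standard error, and it is zero if changes are unrelated to walking or the drug has no effect.

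**What to change.** 1. State in SAP 6.1.3.1 that the primary analysis is within the PD set, as amended by item 2.
2. For COMD03 changes after randomisation, replace the patient-level exclusion by an entry in the SAP 6.1.1 list: drop walk tests after the change and keep earlier ones in the mixed model. SAP 6.2.1 carries this over to pain-free walking distance. Changes before randomisation can stay a patient-level exclusion.
3. Keep the present PD-set analysis as a sensitivity analysis, and add one that uses all observed walk tests regardless of drug change.

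The cost is a SAP amendment before database lock, the route that SAP section 4 already names for updates to Table 4-1, and two extra model runs. No new data collection is proposed.

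Limits: item 2 helps only when the change follows the Week 8 test, and it only reduces bias from decline that was not observed. The all-observed run is the check for earlier changes, but it includes any effect of the changed drug and needs later walk tests to exist. Under protocol 7.2, patients who stop treatment remain in the study, while those who miss more than one dose are discontinued from it and return for safety assessments. The walk-test row of the assessment schedule is not visible, so how many later tests would be available cannot be confirmed.
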